**Table 1: Scheduled visit windows**

Visit name	Period
Day 30	20 – 70 days
Day 90	71-150 days
Day 182	151 – 245 days
Day 246 (last contact attempt)	246 days

## 2.7.3 Care verification

Clinical records will be accessed to determine linkage to care status, timing of linkage to care, ART continuation, retention in care, and HIV RNA results. This will be done through reviewing paper clinic charts, electronic clinic data (tier.net), and electronic laboratory data (NHLs Trackcare system). Linkage between participants and records will be based on matching surname, first name, date of birth, sex, and appropriate date range.

## 2.7.4 Viral loads at 6 months

Participants in the TCAC arm will have 6 month viral loads obtained at the TCAC. Participants in the care as usual (CAU) arm will have a specimen (2mL) drawn at 6 months for viral load assessment.

## 2.8 TCAC post-release procedures

### 2.8.1 TCAC post release contact

Post-release, a study team member will make contact with the participant within 1 week to update contact details and to review attendance at TCAC sessions.

### 2.8.2 TCAC structure

TCACs will provide all the standard services the Department of Health provides for regular community adherence clubs. Similar to community adherence clubs, the TCACs will be affiliated with a clinic and provide visit and medication distribution to the clinic for monitoring and reporting purposes. Routine community adherence club activities include:

- Documentation of visits
- Symptom screen
- Distributing prepacked medications
- Routine laboratory monitoring

TCACs will have a standard structure divided into four parts with each session lasting approximately two hours. Attendance and medication pick-up at the session will be recorded by the facilitator using an electronic attendance log.

### 2.8.3 TCAC frequency and duration

Unlike standard community adherence clubs, participants will be requested to attend monthly sessions. If a TCAC session is missed, the facilitator will send a text message to ask how he or she is doing and to remind him or her of the TCAC sessions. If a participant misses a TCAC session they will have 1 week to collect the pre-packaged medications at the home clinic (in accordance with standard Community Adherence Club protocols). If the member collects the medications from the clinic he or she can return to the TCAC. If a participant misses TCAC sessions for 2 consecutive months, he or she will be considered out of care and will be referred to the local clinic for medication pick-up and medication evaluation. The TCAC facilitator will be responsible for contacting a participant and letting him or her know the care plan.

### 2.8.4 TCAC eligibility

All study participants assigned to the TCAC arm will be eligible for the TCAC. This includes individuals who may not meet community adherence club eligibility criteria. The reason for this approach is that, at present, there is low linkage to care from corrections. Furthermore, those individuals with the greatest adherence and clinic attendance challenges are hypothesized to benefit the most from the TCAC interventions. Thus all released inmates who meet the enrollment criteria will be eligible for TCACs – this is a critical component of the study.

## 2.8.5 TCAC confidentiality

Confidentiality rules will be reviewed for each member at their initial TCAC visit. In addition, each member will be asked to sign a pledge of confidentiality to re-enforce the importance of confidentiality. This approach was used successfully by study team members in prior community adherence club research.

## 2.8.6 TCAC Facilitation

The TCAC will have two facilitators:

- An ex-inmate peer trained in the TCAC facilitation approach, content, and health evaluation.
- A social worker, trained in the facilitation approach, and health evaluation

## 2.8.7 TCAC medical support

Phlebotomy will be provided at TCAC sessions for routine laboratory testing as needed by a professional nurse (registered nurse equivalent). For clinic referrals, a standard symptom and vital sign algorithm will be used for care triage [Appendix – Medical Assessment CRF]. Any participant meeting concern for unmanaged acute or chronic illness will be referred to the local clinic and will be assisted to reach the clinic.

## 2.8.8 TCAC content

A schematic intervention-impact diagram is shown below in Figure 1.

[figure not shown]

Figure 1: Intervention impact model

Part 1: Group discussion and group cognitive behavioral training.

The first 45-60 minutes will involve facilitated discussions among participants related to issues salient to the group. The facilitation of these sessions will seek to teach cognitive behavioral approaches. These approaches can be applied by a participant toward what is most salient to him or her. This may include managing depression, harm reduction, or medication adherence. The overall method is through group cognitive behavioral therapy.

Each session will include discussion on topics of salience to the group such as substance use, alcohol use, ART adherence, family and community relationships, and employment readiness. Facilitation will seek to have participation and involvement from all group members in sharing experiences, strategies, and resources.

#### **Part 2: Individual symptom screen and medication distribution.**

This is expected to take 15-20 minutes. Participants will be called by the facilitators for individual symptom screen and medication distribution (60 day supply as is provided in standard community adherence clubs). Based on the symptom screen, participants may be referred for further evaluation at a local clinic.

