**Barriers to the transition from corrections to community care:** Post-release, ex-inmates are expected to use the referral letter to establish care with Department of Health (DoH) clinics. It is the responsibility of the ex-inmate to identify the clinic and the appropriate days to go, and to advocate for his or her care. There is no active follow-up provided by DCS or DoH to confirm a successful transition, nor is there specific coordination between the DCS and the DoH regarding the release of ex-inmates receiving HIV care. Because of the absence of formal communication between the DCS and the DoH there is no documentation of the transition of care from corrections to community care to inform patient care, care continuum indicators, or quality improvement. The impressive HIV care outcomes observed in correctional settings in South Africa drop off dramatically following release from corrections. Ex-inmates living with HIV encounter unique care transition challenges across the socio-ecological framework. Qualitative and quantitative research conducted by the PI ([name]) and co-I ([name]) with 492 ex-inmates in South Africa, identified several important themes related to the transition in care among ex-inmates. These include the clinic experience, social capital, stigma, substance use (11% of participants with identified drug use), re-incarceration, and economic insecurity. Depression also affects the transition from corrections to community care in the United States, but has not been evaluated in this context in South Africa. Substance use is another barrier to the care transition. Substance use itself interferes with care seeking due to increased impulsivity as well as diminished social capital. As a result of these barriers, at 6-months following release, only 44% had continuity in antiretroviral therapy ([name] unpublished data).

**Barriers to care engagement in the general population in Africa:** Experience with the general population living with HIV provides additional insight regarding potential barriers for ex-inmates. On the individual level of the socio-ecological model, knowledge of HIV, self-efficacy, fatalism,

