#### 2.5.1 Care-as-usual (CAU) study arm

Participants will have a pre-release session with a study team member. The goal of the session is to review study procedures, review contact from the study team or contacting the study team following release, update any changes in contact information, and to encourage post-release linkage to care. This session will occur 1 – 2 weeks prior to release. Per DCS routine, at release, participants will receive a referral letter from the DCS health services and will be dispensed ART (the duration ranges from 30-90 days and is determined by the DCS staff) prior to release.

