## 2.7.2 Ascertainment of linkage to care

Study staff will contact participants to ascertain care status and update contact information at 30, 90 and 182 days from release. Follow up will primarily be telephonic and will rely on participant self-report. The scheduled visit windows are: Day 30 (from 20-70 days), Day 90 (from 71-150 days), and Day 182 (from 151 – 245). The last contact attempt will be made on Day 246. At the Day 182 visit, participants will be asked for in-person contact that will occur either at research offices or at a site convenient to the participant. This study visit will be used to ascertain visit status, socio-demographic data, and to complete surveys on stigma, social capital, and care satisfaction. In addition, a whole blood sample (8mL) will be obtained for HIV RNA quantification (viral load) if there are no clinic obtained HIV RNA results from within 60 days or 182 days post-release. Refer to schedule of CRFs for data collection tools used at each study visit.

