## 2.9.2 Effectiveness of TCACs

**Primary outcome:** The primary outcome of this assessment is the proportion of participants with self-reported care at 6 months either in TCAC or DoH clinical care. Self-reported care at 6 months will be defined as – having at least two post-release HIV care visits 90 days apart with the last visit between 5 and 7 months from release. We will perform an analysis of retention in care at 6 months among all randomized individuals as an intent to treat analysis.

We will also perform an eligible for 6 month follow-up analysis. This analysis will exclude:

- Not released within 3 months of enrollment
- Re-incarcerated within 6 months of release
- Died within 6 months of release
- Withdrawn participation within 6 months of release

**Secondary outcomes:** We will also evaluate the effectiveness of TCACs compared to care-as-usual for the following secondary outcomes:

1. Verified in care at six months
2. Time to linkage to care
3. Linkage to care within 90 days of corrections release
4. HIV RNA <400 c/mL at 6 months - Viral load data at 6 months will be based on routinely collected viral load data (clinic records and the electronic National Health Laboratory System to determine 6 month viral load outcomes, successfully applied in prior studies) augmented by viral loads obtained by the study when 6 month viral load data are not available.
5. Social capital score change
6. Stigma index score change
7. Employment or self-employment

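### The six-month self-report contact can come before the 5–7 month visit window closes, so the primary outcome depends on contact day and on visit frequency, which the intervention sets to monthly in one arm

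*Combined protocol and SAP*

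**What the plan says.** - **Outcome (2.9.2).** The primary effectiveness outcome is "self-reported care at 6 months either in TCAC or DoH clinical care", defined as "having at least two post-release HIV care visits 90 days apart with the last visit between 5 and 7 months from release". Only visit dates enter the rule; ART collection and supply do not.
- **When it is measured (2.7.2, Table 1).** The window is given as "Day 182 (from 151 – 245", in days from release. On the source of the data: "Follow up will primarily be telephonic and will rely on participant self-report".
- **Visit frequency, TCAC (2.8.3, Table 8).** "Unlike standard community adherence clubs, participants will be requested to attend monthly sessions". Table 8 has a session in each of months 1 to 6.
- **Dispensing, TCAC (2.8.8, Part 2).** Sessions include "medication distribution (60 day supply as is provided in standard community adherence clubs". Which sessions dispense is not stated.
- **Visit frequency, CAU.** None is stated. The nearest figures are supplies: 60 days in standard clubs (2.8.8), and at release "the duration ranges from 30-90 days and is determined by the DCS staff" (2.5.1). Section 1.1 gives 15 to 90 days at release, median 30.
- **Analysis.** Neither Table 3 nor section 4.2.2 allows for scheduled visit frequency or contact day.

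**The concern.** Five to seven months is roughly days 153 to 213. A participant contacted on the target day can report only the first half of that window. Whether a visit falls in that half depends on how often visits are scheduled, and the intervention itself fixes that frequency in one arm. Two people who keep every appointment and never run out of ART can then be scored differently.

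At stake is primary objective 2, the between-arm difference in self-reported care, which has a planned test. Table 3 restricts the viral load comparison to those in care, so its denominator could shift by arm if the same definition is used there. The trial is a pilot, but its estimate and procedures are meant to prepare a full RCT.

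**Working it through.** **1. The plan's own figure.** Section 4.1: 120 and 60 randomised, 78% ascertained, so 93.6 and 46.8 analysed. A two-sided test at 0.05 with pooled variance, 0.25 versus 0.49, gives 79.5% power; the detectable difference from 0.25 is 0.242. The stated 80% and 0.24 reproduce, and this point does not affect them.

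**2. One calendar, first visit on day 25, all visits kept.**
- Monthly: days 25, 55, 85, 115, 145, 175, 205, 235.
- Every 60 days: days 25, 85, 145, 205.

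Contact on day 182: the monthly attender passes (day 175). The 60-day attender, last seen on day 145, fails. Contact on day 213: both pass on day 205. Contact on day 245 with the last-visit rule read literally: the monthly attender fails (last visit day 235) and the 60-day attender passes (last visit day 205).

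**3. Share scored in care among perfect attenders.** Assumptions: visits every R days (30, 60 or 90), first visit uniform over the first R days, and any visit inside the window counts. With these intervals the 90-day spacing is then always met. So share = (days from 153 to the earlier of contact and 213) / R, capped at 1.

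| Contact day | R = 30 | R = 60 | R = 90 |
|---|---|---|---|
| 182 | 100% | 30/60 = 50% | 30/90 = 33% |
| 198 | 100% | 46/60 = 77% | 46/90 = 51% |
| 213 or later | 100% | 100% | 61/90 = 68% |
| Uniform over 151–245 | 82.6% | 66.8% | 44.9% |

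Counting from day 152 instead changes these by about 1 to 2 points. At an early contact even monthly attenders mostly fail: on day 160 the shares are 8/30 = 27%, 8/60 = 13% and 8/90 = 9%.

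**4. False difference.** Section 1.1 reports of a prior cohort that "at 6-months following release, only 44% had continuity in antiretroviral therapy". Assume 44% in both arms, with every TCAC continuer attending monthly. False difference = 0.44 × (share at R = 30 − share at the CAU interval).
- Day 182: 0; 0.44 × 0.50 = 0.22; 0.44 × 0.667 = 0.29.
- Day 198: 0; 0.44 × 0.233 = 0.10; 0.44 × 0.489 = 0.22.
- Day 213 or later: 0; 0; 0.44 × 0.322 = 0.14.
- Uniform contact: 0; 0.44 × (0.826 − 0.668) = 0.07; 0.44 × (0.826 − 0.449) = 0.17.

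**5. Literal last-visit rule.** At a day-245 contact the last monthly visit falls on days 216–245, so 0% pass. The last 60-day visit falls on days 186–245, of which 28 of 60 (47%) are by day 213. The false difference is 0.44 × (0 − 0.467) = −0.21, favouring CAU. With uniform contact the literal shares are 64.2% (30-day) and 57.6% (60-day), a difference of 0.44 × 0.066 = 0.03 favouring the TCAC.

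**6. Effect on the test.** Exact enumeration of the chi-square test, 94 versus 47, nominal 0.05: equal 44% rejects 4.9% of the time; 0.44 v 0.22 rejects about 75%; 0.363 v 0.294 (60-day visits, uniform contact) about 12%.

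**The case against.** The documents do not give the CAU interval. The 60-day figure belongs to clubs for stable patients, the 30–90 days are release supplies, and the only central figure, a 30-day median release supply, would suggest no gap if visits followed it. This stands: the size is conditional.

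The calculation also makes every TCAC continuer a monthly attender. Section 4.1 expects 40–66% to transition to a TCAC, and DoH visits count for the others, so the figures are upper values for each interval and contact day. The day-245 reversal likewise needs monthly visits to continue after month 6, when section 2.8.11 moves people to DoH models.

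Retention in care is a legitimate target, monthly contact is part of the intervention, and the rule is worded identically for both arms. That supports keeping a visit-based outcome. It does not answer the point that a perfect 60- or 90-day attender is retained and can still fail. Verified care and viral load are secondary outcomes that protect only in part: verified care has no definition of its own, and viral load is limited to those in care.

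Three stronger readings are tempting:
- *The 60-day supply set against monthly sessions is the cause.* It is not. The rule has no supply term, and the result would be the same with 30-day packs.
- *There is a bias of about 24 points in favour of the TCAC.* That size needs 60-day CAU visits and contact near day 182, and the direction is not fixed. The 0.24 in section 4.1 is also for being in care with an undetectable viral load, a different outcome, and is called illustrative.
- *The outcome should be ART supply.* The plan chose retention. Days supplied plus a grace period would favour the arm given larger packs: with 30 days' grace, a last collection on day 95 reaches day 185 with a 60-day pack but day 155 with a 30-day pack.

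**Conclusion.** The point holds as a flaw in how the outcome definition and the contact window fit together. The score depends on contact day and scheduled visit frequency, and frequency is set by the intervention in one arm. Given 44% continuity in both arms and full monthly attendance by TCAC continuers, the false difference at day 182 runs from 0 to about 29 points as the assumed CAU interval runs from 30 to 90 days. Over the whole contact window the 60-day case falls to about 7 points, and later contact removes it. The literal wording can reverse the sign. The documents therefore support neither a fixed size nor a fixed direction, and a reader should not infer that the trial is biased toward the TCAC by any particular amount. What they support is that the planned comparison cannot separate retention from visit schedule, and that this can be corrected cheaply before data collection.

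**What to change.** **Preferred.** Keep a visit-based retention outcome. In 2.9.2 and 2.7.2, ascertain it at a contact on or after day 182, up to day 245, and count any HIV care visit (TCAC or DoH) in the 90 days before that contact, the same way in both arms. Anyone keeping 30-, 60- or 90-day visits has a visit within that look-back at any such contact, so all score alike.

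**Alternative.** Keep the 5–7 month window, take the visit history on or after day 213, and require a visit in the window instead of the last visit. This removes the gap for 30- and 60-day visits. For 90-day visits 68% would pass, leaving about 14 points.

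Either way, keep the current definition as a sensitivity analysis, and state the usual DoH visit interval and which TCAC sessions dispense. ART-supply scoring should be at most supplementary.

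**Cost.** Wording changes, with no extra visits or participants. Contacts before the new start day would no longer count for the outcome, which may slightly lower ascertainment against the 75% follow-up target. A 90-day look-back is also a looser definition of retention.

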#### **Part 3: Snacks/lunch: 15 – 20 minutes**

#### **Part 4: Life skills training**

This will use a structured curriculum delivered by the facilitators or invited guest speakers. Topics will include: sustainable livelihoods, with sessions and materials on education/bursaries, finding and maintaining jobs, income generation, and saving and emergency funds; transitional support, with sessions and materials on transitional needs, transitional planning, and incarceration stigma and disclosure; and HIV care and treatment, with sessions and materials on HIV/AIDS, medication adherence, nutrition, treatment as prevention, and HIV stigma and disclosure. These skills training will partially use material adapted from ongoing routine programs in South Africa (e.g. Stepping Stones).

#### **2.8.9 Schedule of TCAC medical evaluations**

In addition to the standard structured group activities, there is a list of individual activities focused on health assessment and ART management and based on duration from release. These components are as follows:

1. **First session:** Health and ART history review, ASSIST substance use (alcohol and other drugs) screen, PHQ-9 depression screen, social capital, and stigma screens. The results of these tools will be used for guiding referrals and session services. This screening will occur on arrival at the TCAC session.
2. **Every session:** At every session the following will be performed: symptom screen, weight measurement. An algorithm for action or non-action will be developed. Based on the

algorithm, study staff may collect sputum, or refer participants to a primary care clinic based on the symptom screen and weight.

3. **At 6 months:** Laboratory assessment with HIV RNA, creatinine, and CD4 count. In addition, starting at 6 months, participants will be evaluated for transition to standard services including community adherence club, community chronic medication distribution, or clinic medication fast lanes.

#### 2.8.10 Ad-hoc participant specific components

- Ad hoc counselling or case management / social work needs
- Care documentation: standard DoH stationary will be used to record TCAC attendance, symptom screen, and medication receipt.
- Missed visits: Any participant not reporting to a session and not collecting medication within 1 week will be reported to the dispensing clinic and will be contacted by the facilitator (either telephonically or with a home visit)

#### 2.8.11 TCAC completion & transition to regular differentiated care

At the end of 6 months individuals will be encouraged to join the appropriate DoH differentiated care model. These include standard clinic care, clinic fast lanes, community dispensing of chronic care medications, and standard community adherence clubs. The model will depend on the determination of the clinic.

### 2.9 Outcomes and Ascertainment

#### 2.9.1 Feasibility of TCACs

The goal of this assessment is both to evaluate the feasibility of implementing the TCAC and of endpoint ascertainment for a larger clinical trial of TCAC implementation.

Specific feasibility considerations are:

- 1) The proportion of participants who are able to navigate to the TCAC as defined by success with intended first TCAC visit
- 2) Success of the study team to ascertain six month linkage to care status
- 3) Ability to use social capital and stigma index tools and assess HIV RNA level at six months.

Success will be based on *a priori* targets of  $\geq 90\%$  of those attempting to attend a TCAC session able to find the location, successful follow-up of  $\geq 75\%$  of participants, and viral load ascertainment for  $\geq 95\%$  of participants in care.

**Table 2: Feasibility Indicators**

Numerator	Denominator	Measure
-----------	-------------	---------

Number with first TCAC visit	Total in TCAC arm	Proportion
Number in TCAC arm with visit first to a clinic (not TCAC)	Total in TCAC arm	Proportion
Number in TCAC at 6 months (at least 2 visits)	Number with first TCAC visits	Proportion
Number in TCAC at 6 months	Number in TCAC arm	Proportion
Number with no more than two missed visits in 6 months	Number in TCAC arm	Proportion
Proportion of all participants with successful 6month care ascertainment assessed	All study participants	Proportion
Proportion of all participants with 6 m social capital questionnaire and stigma scale	All study participants	Proportion
Proportion among those in care with 6m VL ascertainment	All study participants	Proportion

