#### 2.4.2 Randomization

We will perform individual randomization blocked by correctional facility. Study staff will open numbered envelopes with the allocation following enrollment. Participants will be randomized 1:2 to either the standard of care or the TCAC using sequential envelopes with study arm determination sealed inside (blocked by study site and based on random number generation). Participants and members of the research team recruiting and implementing the strategy will be unmasked to randomization assignment due to the behavioral nature of the strategy and need for team members to explain the study arm procedures to participants. Study assignments will be masked to staff performing outcome assessments and the investigators until all outcome data have been collected.

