**Table 3: Effectiveness outcomes**

Primary outcome	Self-reported in care at six months by arm	Test of proportions (chi-square)
Secondary outcomes	Self-reported linkage to care by 90 days by arm	Test of proportions (chi-square)
	Clinical record verified in care at six months by arm	Test of proportions (chi-square)
	HIV RNA <400c/mL for those in care by arm	Test of proportions (chi-square)
	Social capital score by arm	Test of medians (Wilcoxon rank sum)
	Stigma index score by arm	Test of medians (Wilcoxon rank sum)
	Employed or self-employed by arm	Test of proportions (chi-square)

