### 4.1 Sample size

As a study of feasibility and acceptability we have selected a sample size that, based on prior experience, can easily be recruited within 6 months. From the most recent prior work, we recruited approximately 35 inmates per month (approximately 2% declined participation). Over a 6 month period this would result in 210 *released* inmates. To be conservative, we will seek to recruit only 50% of the recruitment rate of the prior study, representing a total of 60 participants into the standard of care and 120 in the TCAC arm. We will continue recruiting until we have reached 180 released inmates.

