**Table 4 : Sample size for TCAC evaluation**

Arm	Sample size
Care as usual	60
TCAC	120

Recruiting 120 in the TCAC arm will provide four TCACs with 12-20 participants each (assuming 40 to 66% successful transition in care to TCACs among participants in that arm). The 1:2 enrollment provides a greater population in the TCAC arm for assessing acceptability. This sample size has an 80% power with an alpha of 0.05 to identify an approximate difference in proportion meeting the primary outcome (in care with an undetectable viral load at 6 months) of 0.24 (e.g. 0.25 versus 0.49 meeting the primary outcome) assuming successful outcome ascertainment for 78% of participants (our success in a prior study) (Figure 2). We note that this is not an effectiveness study and we present these calculations purely to illustrate the power.

[figure not shown]

Figure 2: Proportions in care in CAU and TCAC that study is powered to detect with alpha of 0.05

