## 4.2 Analysis

### 4.2.1 Feasibility

Success will be based on *a priori* targets of  $\geq 90\%$  of those attempting to attend a TCAC session able to find the location, successful follow-up of  $\geq 75\%$  of participants (based on the challenging nature of follow-up of this population our prior work with 75% follow-up), and viral load ascertainment for  $\geq 95\%$  of participants in care.

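### The 75% follow-up target is pooled over a 1:2 allocation, so endpoint ascertainment can be called feasible while the care-as-usual arm is well below 75%

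*Combined protocol and SAP*

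**What the plan says.** Section 1.2 lists feasibility of implementation and of endpoint ascertainment as the first primary objective. It describes the trial being prepared for as a randomized comparison of TCAC with traditional care. Section 2.9.1 repeats the purpose: to "evaluate the feasibility of implementing the TCAC and of endpoint ascertainment for a larger clinical trial of TCAC implementation".

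Sections 2.9.1 and 4.2.1 set the success target at follow-up of at least 75% of participants, with no arm named. Section 4.2.1 justifies the level as "based on the challenging nature of follow-up of this population our prior work with 75% follow-up". The matching row of Table 2 is "Proportion of all participants with successful 6month care ascertainment assessed", and its denominator is the whole study. Two more rows, on the six-month questionnaires and on viral load, also carry a whole-study denominator.

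On allocation, section 2.4.2 states "Participants will be randomized 1:2 to either the standard of care or the TCAC", and section 4.1 gives "a total of 60 participants into the standard of care and 120 in the TCAC arm".

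No section sets a follow-up target for the CAU arm, a limit on the difference between arms, or a follow-up indicator by arm. Table 3 is by arm but lists effectiveness outcomes only. The other two feasibility targets do not fill the gap: one concerns finding the TCAC venue, and the other covers viral load only among people in care.

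**The concern.** A comparative trial needs its endpoint in both arms. A pooled proportion in which two thirds of the people come from one arm says little about the other.

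The arms are also not followed identically. Only the TCAC arm has monthly sessions with an attendance log (2.8.2, 2.8.3), a text after a missed session (2.8.3), telephone or home-visit contact when medication is not collected (2.8.10), and the six-month viral load taken at the club (2.7.4). Better ascertainment in that arm is therefore plausible from the design itself.

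At stake is the answer to Objective 1. The pilot could report that ascertainment succeeded without showing that the control arm can be followed. Unequal ascertainment costs power in the later trial and, depending on how missing outcomes are handled, can bias the comparison.

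**Working it through.** **Inputs.** Arm sizes 60 and 120 (4.1); target 75% (2.9.1, 4.2.1); club uptake of 40–66% in the TCAC arm, ascertainment of 78% and proportions of 0.25 versus 0.49 (text under Table 4); 44% with ART continuity at six months in prior work (1.1). The test is taken as a two-sided chi-square at 0.05; sidedness is not stated.

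**1. The plan's own power figure.** It applies one 78% ascertainment rate to everyone: 0.78 × 60 = 46.8 and 0.78 × 120 = 93.6. The pooled proportion is (46.8 × 0.25 + 93.6 × 0.49)/140.4 = 0.41. Then z = [0.24 − 1.96 × √(0.41 × 0.59 × (1/46.8 + 1/93.6))] / √(0.25 × 0.75/46.8 + 0.49 × 0.51/93.6) = (0.24 − 0.1726)/0.0817 = 0.825, a power of 79.5%. The stated 80% reproduces and is not in dispute.

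**2. What the pooled target allows.** 0.75 × 180 = 135. If t is the TCAC rate, the CAU rate that still passes is (135 − 120t)/60.

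| TCAC | CAU still passing | Power for 0.25 v 0.49 |
|---|---|---|
| 75% (90/120) | 75% (45/60) | 77.9% |
| 80% (96/120) | 65% (39/60) | 74.3% |
| 85% (102/120) | 55% (33/60) | 69.3% |

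Every row has the same pooled 75%. Under 1:1 allocation, TCAC at 85% would still require CAU at 2 × 75 − 85 = 65%, so the 1:2 ratio makes the masking worse.

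**3. How often this could happen.** The documents give no by-arm rates, so a model is needed. Assume that all club attenders are ascertained and that the rest of the TCAC arm is followed like CAU. With uptake u and CAU rate c, the TCAC rate is u + (1 − u)c. The pass chance is the binomial probability of at least 135 ascertained in total.

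| True CAU rate | Uptake | TCAC rate | Pooled rule passes |
|---|---|---|---|
| 65% | 40% | 0.40 + 0.60 × 0.65 = 79% | about 46% |
| 65% | 66% | 0.66 + 0.34 × 0.65 = 88% | about 98% |
| 55% | 40% | 0.40 + 0.60 × 0.55 = 73% | about 1% |
| 55% | 66% | 0.66 + 0.34 × 0.55 = 85% | about 51% |

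Treating the number of attenders as fixed or as random moves these by about one point or less.

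**4. Illustration of bias.** The plan does not say how unascertained participants count in the intent-to-treat analysis. Assume that they count as not in care and that true care is 44% in both arms. At 80/65 the apparent rates are 0.44 × 0.80 = 35.2% and 0.44 × 0.65 = 28.6%, a spurious 6.6 points. At 85/55 they are 37.4% and 24.2%, a spurious 13.2 points.

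**5. Cost of a hard cutoff in each arm.** Requiring at least 45/60 and at least 90/120 at a true 78% in both arms gives a success chance of 0.768 × 0.818 = 0.63, against 0.855 for the pooled rule.

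**6. Precision.** At 75%, the 95% half-width for CAU is 1.96 × √(0.75 × 0.25/60) = 0.11. For the between-arm difference it is 1.96 × √(0.75 × 0.25/60 + 0.75 × 0.25/120) = 0.13.

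**The case against.** The shared follow-up is substantial. Both arms have a tracing plan with next of kin, an airtime incentive for making contact and tracing through community corrections (2.7). Both have a first contact by day 15 and two-weekly messages (2.7.1), contacts at days 30, 90 and 182 with the last sought in person (2.7.2), and review of clinic and laboratory records (2.7.3). Outcome assessors are to be masked (2.4.2), which suggests that ascertainment is separate from the club staff. This stands and argues against assuming a very large gap. It does not remove the contact points that only the TCAC arm has. Record review may also help less than it seems, because the primary outcome is self-reported care and successful ascertainment is not defined.

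A reader might infer that the pilot would trigger the full trial with about half of the control arm missing, for example with TCAC at 90% and CAU at 45%. The arithmetic permits that, but the documents do not support it as an expectation. Their only follow-up figures are 75% and 78%, from prior work. A 90% TCAC rate beside 45% in CAU would, under the model above, need uptake of (0.90 − 0.45)/0.55 = 82%, beyond the stated 40–66%. Nor does any section make the target an automatic trigger: it defines feasibility success, by-arm reporting is not forbidden, and the monitoring board sees outcome data every six months.

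The objection that a 75% pass rule in each arm would often fail a feasible trial also stands (step 5), and the fix avoids that rule.

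**Conclusion.** The concern holds as a gap in the decision rule. The stated criterion for endpoint ascertainment can be met with CAU at 55–65% when TCAC is at 85–80%. Under the stated uptake model, the pooled rule would pass about 46–98% of the time at a true CAU rate of 65%, and about 1–51% at 55%. Over the same range, with 135 ascertained throughout, power for the protocol's own example falls from 77.9% to 74.3% or 69.3%.

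These results rest on three assumptions: that the denominator is the 180 released participants, that club attenders are all ascertained, and that non-attenders are followed like CAU. The bias figures rest further on counting missing as not in care.

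The documents do not establish that CAU follow-up will be poor, and they set no minimum per-arm follow-up for the full trial. To call the later comparison uninterpretable would therefore go too far. What they show is that the rule as written would not reveal a shortfall in the arm where it is more likely.

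**What to change.** In 2.9.1, 4.2.1 and Table 2:

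- Split the three rows with a whole-study denominator by arm.
- Report each arm's six-month ascertainment and the between-arm difference, with 95% confidence intervals.
- State that the conclusion on endpoint ascertainment rests on the arm-specific results: the CAU estimate and a maximum between-arm gap, fixed before outcome data are seen, are read alongside the pooled 75%. The documents give no basis for the size of the gap, so the sponsor should choose and justify it, bearing in mind the 13-point half-width in step 6.
- Report viral-load ascertainment by arm descriptively, without a 95% threshold in each arm. With 25–44% of 60 CAU participants in care, that threshold would rest on about 15–26 people and allow no more than one missing result.

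The change is wording only and needs no new data. The costs are an imprecise CAU estimate (about ±11 points from 60 people) and a conclusion that is somewhat harder to call a success. A hard 75% pass rule in each arm is not required.
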